#### 6.7.4. Multiple Assessments

Where multiple planned scheduled measurements are recorded for a given time point (eg, electrocardiograms [ECGs]), the mean of the measurements will be calculated and used in any derivation of summary statistics. All available data will be listed.

When multiple visits occur within the same window, the scheduled visit will be used in analysis if available. If no scheduled visit occurs within the window and an unscheduled visit(s) and/or early termination visit occur within the window, the analysis visit closest to the target day will be selected for use in analysis. If deemed appropriate by the Sponsor (eg, in the case of a retest), unscheduled visits may be chosen for analysis given documentation of the desired visit from the Sponsor. Results from unscheduled visits will be eligible for inclusion in analyses of worst post-baseline results. Listings will display all visits as recorded on the CRF, including the date and study day. All available data including any totals, domains, or subscales of scale assessments summarized will be listed.

### 6.7.5. Derived Efficacy Endpoints

#### 6.7.5.1. Attack Rate

#### **General Formula for Attack Rate**

In general, the formula for computing an attack rate is the number of attacks meeting the attack criteria divided by the duration of treatment during the reporting period of interest.

duration of treatment during the reporting period of interest = the last day in the reporting period - the first day in the reporting period + 1

Attack Rate 
$$\left(\frac{attacks}{month}\right)$$
 During Reporting Period of Interest  
=  $\frac{\text{Number of Attacks * 28}}{\text{Duration of Treatment During Reporting Period in Days}}$ 

If the subject discontinues treatment early, any attacks that occur within 24 hours after last dose will be counted in the calculation of attack rate and the additional 24 hour period will be included in the duration of the reporting period.

#### Subject-Reported Attack Rate

Diary entries for attacks are considered subject-reported attacks. The count of subject-reported attacks can differ from the count of confirmed attacks. In Parts 1 and 2, the investigator reviews each attack and either confirms it as an attack or rejects it as an attack. For Part 3, there is no investigator review of attacks, but an adjusted subject-reported attack rate will be computed based on a list of programmable requirements.

Subject-reported attack rates will be computed for Parts 1, 2, and 3.

#### Adjusted Subject-Reported Attack Rate for Part 3

Because there is no investigator-confirmation of attacks during Part 3, an adjusted subject-reported attack rate will be computed.

Subject-reported attacks must meet the following criteria (applied in order) for inclusion in the adjusted subject-reported rate computation:

- Attack must include at least 1 symptom of swelling
- Subject response to diary question, "In retrospect, could there be an alternative explanation for your symptoms other than an HAE attack (ie, allergic reaction, viral cold, etc)?" must be "no"
- Attack must be unique (attack begins > 24 hours from end of the prior attack), otherwise the event will be combined with and treated as a continuation of the preceding attack
- If untreated, attack must have a duration > 24 hours.

Adjusted subject-reported attack rates will be computed for the following reporting periods and expressed in units of attacks/month where 1 month = 28 days:

- Part 3, by month
- Part 3, entire dosing period

For adjusted subject-reported attack rates by month, months will be defined in blocks of 28 days, beginning on the first day of dosing in Part 3. If the subject discontinues treatment early, any attacks that occur within 24 hours after last dose will be counted in the calculation of subject-reported adjusted attack rate and the additional 24 hour-period will be included in the duration of the reporting period.

#### **Confirmed Attack Rate**

Confirmed attack rates will be computed based on the number of confirmed attacks that occur during the reporting period of interest.

Confirmed attack rates will be computed for the following reporting periods and expressed in units of attacks/month where 1 month = 28 days:

- Parts 1 and 2, By month
- Parts 1 and 2, Entire dosing period
- Parts 1 and 2, Effective dosing period

Confirmed attack rates will be computed for Part 1 and at the end of Part 2. For confirmed attack rates by month, months will be defined in blocks of 28 days, beginning on Day 1, the day of first dose. The entire dosing period begins on Day 1 or adjusted Day 1 during Part 2 for subjects originally randomized to placebo. The effective dosing period similarly begins on Day 8 or adjusted Day 8. Part 1 continues until the time of Part 2 dose. Part 2 continues until the time of first dose for Part 3. Investigator confirmation is not done in Part 3 and so confirmed attack rate

will not be computed for Part 3. If the subject discontinues treatment early, the reporting period will continue through 24 hours post last dose and any attacks that occur within 24 hours after last dose will be counted in the calculation of attack rate. If there are confirmed attacks in the eCRF without corresponding diary information, as may happen if a subject verbally reports an attack to an investigator but does not enter it into the ediary, the attack will be counted.

For sensitivity analyses for missing data for the Part 1 primary analysis, confirmed attack rates for the entire dosing period for subjects who discontinue treatment early will be re-computed as a weighted average of the observed post-treatment discontinuation attack rate and an imputed attack rate for periods of missing data post-treatment discontinuation. Details are provided in Section 6.8.1.

### **Confirmed Attack Rate by Location**

Confirmed abdominal-only, peripheral, and mixed attack rates will be computed using the location definitions provided in Section 6.7.5.9.

### **Adjusted Confirmed Attack Rate**

An adjusted confirmed attack rate will be computed for use in the determination of the 50% responder endpoint comparing post-baseline attack rates to baseline attack rates. For the adjusted confirmed attack rate, the 2 additional requirements for confirmation of attack rates used during screening will be applied to post-baseline confirmed attacks to determine the number of confirmed attacks meeting the additional requirements. The additional requirements are:

- The attacks are unique, which is defined as an attack that does not begin within 48 hours of the end of a previous attack.
- The attacks must have either been treated, required medical attention or be documented to cause functional impairment based on subject entry in the diary. Functional impairment is defined as the subject being unable to perform their daily activities without restriction (ie, subject records that they are at least slightly restricted in their daily activities during their HAE attack).

#### 6.7.5.2. Number and Percentage of Subjects Who Are Attack Free over Entire Dosing Period and Effective Dosing Period

The following attack-free endpoints will be derived for the entire dosing period and for the effective dosing period for Parts 1 and 2:

• The number and percentage of subjects with no confirmed attacks during the period of interest. Subjects with no confirmed attacks who discontinue before the end of the planned treatment period are not considered attack-free.

The attack-free rate for active treatment for subjects originally randomized to placebo will be based on the 24-Week period during Part 2.

### 6.7.5.3. Number and Proportion of Days with Angioedema Symptoms

The number of days with angioedema symptoms is the sum of the days during the reporting period for which at least 1 symptom is reported during an investigator-confirmed HAE attack.

This endpoint will be determined for Parts 1 and 2 as investigator-confirmation will not be calculated for Part 3. As with the calculation of attack rate, if the subject discontinues treatment during the reporting period, any symptoms during confirmed attacks that occur within 24 hours after last dose will be counted in the calculation of days with angioedema symptoms and the additional 24-hour-period will be included in the duration of the reporting period.

The percentage of days with angioedema symptoms is derived as the number of days with angioedema symptoms divided by the duration of the treatment period of interest.

## 6.7.5.4. Responder Endpoint

A subject is defined as being a responder to study treatment if the rate of adjusted confirmed attacks during study treatment represents at least a 50% relative reduction compared with the baseline attack rate as defined in Section 6.6.1.

The relative reduction is calculated for Part 1 as:

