# Relative reduction Baseline attack rate – Adjusted Confirmed attack rate on treatment Baseline attack rate × 100%

where the adjusted confirmed attack rate while on study treatment is computed as shown in Section 6.7.5.1.

A subject is classified as a responder if the relative reduction in monthly attack rate for Part 1 is  $\geq$  50%. Otherwise, the subject is classified as a non-responder.

Responder analysis will be conducted for Part 1 only.

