## 8.8.2. Proportion of Responders to Study Drug.

Subjects will be classified as responders or non-responders for Part 1 as discussed in Section 6.7.5.4. A responder is defined as a subject who has at least a 50% relative reduction in the rate of investigator-confirmed HAE attacks meeting the stricter screening criteria during treatment compared with the baseline attack rate. A summary of the number and proportion of responders by study treatment will be produced. Logistic regression with responder status as the outcome variable and treatment and baseline attack rate as independent variables in the model will be used to compare each active treatment to placebo treatment. Point estimates of the odds ratios for response comparing 110 mg to placebo and 150 mg to placebo will be calculated along with corresponding 95% CIs. If the proportion of responders is near zero for the placebo treatment (or for either active treatment), logistic regression may not be an appropriate methodology for analysis and Fisher's exact test will be used in place of logistic regression.

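### The 50% responder rule has no minimum exposure and no rule for discontinuation, so a few attack-free days can count as a 24-week response

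*SAP*

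**What the plan says.** SAP 6.7.5.4 defines a responder as a subject whose adjusted confirmed attack rate on study treatment shows "at least a 50% relative reduction compared with the baseline attack rate". The only other branch is: "Otherwise, the subject is classified as a non-responder". Section 8.8.2 repeats the rule as "at least a 50% relative reduction in the rate of investigator-confirmed HAE attacks meeting the stricter screening criteria during treatment" and analyses it with "Logistic regression with responder status as the outcome variable and treatment and baseline attack rate as independent variables in the model", giving odds ratios and 95% confidence intervals for each dose against placebo.

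The rate comes from 6.7.5.1, which defines it as "the number of attacks meeting the attack criteria divided by the duration of treatment during the reporting period of interest". When treatment stops early, the only adjustment is that "any attacks that occur within 24 hours after last dose will be counted in the calculation of attack rate", with the same 24 hours added to the duration. The adjusted confirmed attack rate in 6.7.5.1 tightens what counts as an attack but sets no minimum exposure.

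For the attack-free endpoint, 6.7.5.2 adds a safeguard, which 8.8.1 repeats: "Subjects with no confirmed attacks who discontinue before the end of the planned treatment period are not considered attack-free". Neither 6.7.5.4 nor 8.8.2 has an equivalent sentence.

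**The concern.** A subject who takes drug for seven days without an attack has an on-treatment rate of 0, a relative reduction of 100%, and so is a responder. The same subject fails the attack-free endpoint. If that subject stopped because of rash, an adverse event or perceived lack of efficacy, the imputation analysis of the primary endpoint (6.8.1 and Table 13) would fill the unobserved time with the median rate of the worst quartile of the arm, or the subject's own rate if worse.

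The primary Poisson model carries log duration as an offset, so a week of data has little weight there. The logistic responder model gives that week the same weight as 24 weeks. The reported percentages, and the odds ratios against placebo, therefore depend on how many subjects stop early, when they stop, and whether this differs by arm. The imputation and tipping-point analyses in 6.8.1 and 8.6.2 are specified for the primary attack rate and do not cover this endpoint.

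**Working it through.** **The plan's own figures.** The SAP gives no figure for the responder endpoint. The nearest inputs are in 4.3.1. A two-sample t-test with 32 per arm, a difference of 0.5 and an SD of 0.55 gives 94.7% power (stated: 94%). Allowing for 20% dropout, 32 / 0.80 = 40 per arm, as stated.

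**Inputs.** From the SAP: the 50% threshold, a 28-day month, 168 days in Part 1, 24 hours added after an early stop, 40 per arm, and a 20% dropout allowance. Assumed, because the documents do not give them: Poisson attacks, true baseline rates of 1 to 4 per 28 days, the true reduction, and the stopping day. Stopping on Day 7 counts as 8 days; Day 14 counts as 15.

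**Formula.** With baseline rate b, true reduction r, and k attacks in D days, the subject responds if k × 28 / D ≤ 0.5 × b. The count k is Poisson with mean b(1 − r)D / 28.

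**No effect, b = 3.**
- D = 8: mean 24/28 = 0.857. One attack gives a rate of 3.5, above 1.5, so only k = 0 qualifies: exp(−0.857) = 42.4%.
- D = 15: mean 1.607. One attack gives 1.87, so again only k = 0 qualifies: exp(−1.607) = 20.0%.
- D = 168: mean 18, up to 9 attacks allowed: 1.5%.

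**Probability of being classed a responder:**

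| Baseline per 28 days | True reduction | 8 days | 15 days | 168 days |
|---|---|---|---|---|
| 2 | 0% | 56.5% | 34.3% | 4.6% |
| 3 | 0% | 42.4% | 20.0% | 1.5% |
| 3 | 50% | 65.1% | 44.8% | 58.7% |
| 2 | 75% | 86.7% | 76.5% | 96.6% |
| 3 | 75% | 80.7% | 66.9% | 98.3% |

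With no effect, the 8-day figure across baselines 1 to 4 runs from 75.1% down to 31.9%; the 168-day figure runs from 15.1% down to 0.5%.

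**Effect on an arm.**
- No effect, b = 3, 20% stopping at Day 14: 0.2 × 20.05% + 0.8 × 1.54% = 5.2%. With stoppers as non-responders: 0.8 × 1.54% = 1.2%.
- Eight of 40 with 8 days counted, b = 2: 15.0% under the current rule against 3.7% with stoppers as non-responders (no effect); 63.5% against 48.5% (50% reduction); 94.7% against 77.3% (75% reduction).
- Two of 40 with 8 days counted, no effect, b from 1 to 4: the gap is 1.6 to 3.8 points.

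**Effect on the comparison.** Suppose b = 3, no placebo subject stops, and 20% of the active arm stops at Day 14. With an inert drug, the arms show 5.2% and 1.5%, an odds ratio of (0.0524/0.9476) / (0.0154/0.9846) = 3.5 where the truth is 1. With a true 75% reduction, the active arm shows 0.2 × 66.9% + 0.8 × 98.3% = 92.0% instead of 98.3%, so the odds ratio is understated. The bias can run either way.

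**The case against.** A reader might infer that early stopping inflates the response rate in general, and that the active arm gains because its tolerability failures are scored as efficacy. The documents do not support that. Near the planning effects in 4.3.1 (a 50% reduction assumed, 73.8% seen in the earlier study), stopping at Day 14 lowers the chance of response at baselines 2 and 3, because one early attack makes a short-exposure subject a non-responder. Nor do the documents give evidence that early stopping will differ by arm.

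The no-effect figures also treat baseline as the known true rate. In fact it is measured in a run-in selected for at least two or three attacks, so regression to the mean applies. A simulation of an inert drug, with randomization on the earliest qualifying day and true rates of 1.5 to 3, gives 18 to 29% responding on 168 days and 36 to 50% on 15 days. The bias remains, but in relative terms it is much smaller.

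The difference from the attack-free endpoint can be defended. Having no attacks over 24 weeks requires the full period, whereas response is a rate during treatment, in line with the on-treatment estimand in 8.6.1. This makes the current rule a possible choice. It does not make a week of data informative about 24 weeks, and the SAP does not state the choice or its consequence.

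A per-protocol version of the relative-reduction table is listed (14.2.6.1.2). That population must complete Part 1, so the table leaves out early leavers instead of counting them as failures, and is only a partial check. Exposure and subject-level listings would show short-exposure responders, but only to someone looking for them.

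The SAP is for Study 302 and the supplied protocol is for Study 202, so a rule in the 302 protocol cannot be excluded. The SAP's list of changes from protocol mentions none.

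**Conclusion.** The gap is real: the responder rule classifies subjects on any length of exposure and does not address discontinuation. Against a rule that counts early stoppers as non-responders, it can only raise the response rate. Against 24-week status, it inflates response when the effect is nil or weak, is mixed at about a 50% reduction, and can understate response when the effect is strong. A claim of inflation in one direction would go too far. The odds ratio against placebo can be biased either way if early stopping differs by arm.

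The sizes rest on a Poisson model and on assumed baseline rates and stopping days. The SAP's 20% is a conservative dropout allowance with no timing attached, so the cases in which all dropouts stop within two weeks are extreme. The endpoint is exploratory (3.2.3) and outside the testing hierarchy (8.5), so the primary and secondary conclusions do not depend on it. The change is worth making because it is cheap and follows a convention the SAP already uses.

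**What to change.** Add one sentence to 6.7.5.4 and repeat it in 8.8.2: subjects who discontinue study treatment before the end of Part 1 are classified as non-responders, as 6.7.5.2 does for attack-free status. Keep the current on-treatment rule as a sensitivity display. The same sentence should give the status of randomized subjects who are never dosed, since they have no on-treatment duration.

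No new data are needed, but the cost in reported response is not trivial. If 20% of an arm stops very early, response falls by about 15 to 17 points at baseline 2 with a true reduction of 50 to 75% (11 to 19 points across baselines 1 to 4). With two early stoppers per 40 and an inert drug, it falls by about 2 to 4 points. The rule is also blunt: a subject with a good response who stops late, or for a reason unrelated to the drug, becomes a failure. The sensitivity display lets readers see how much of the difference comes from such subjects.

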# Relative reduction Baseline attack rate – Adjusted Confirmed attack rate on treatment Baseline attack rate × 100%

where the adjusted confirmed attack rate while on study treatment is computed as shown in Section 6.7.5.1.

A subject is classified as a responder if the relative reduction in monthly attack rate for Part 1 is  $\geq$  50%. Otherwise, the subject is classified as a non-responder.

Responder analysis will be conducted for Part 1 only.

# 6.7.5.5. Attack Duration

The duration of each confirmed on-treatment attack will be calculated in hours, based on the start and stop date and time of the confirmed attack (time the attack finished). Investigators have the option to count more than 1 subject-reported attack as a single confirmed attack. For a confirmed attack that includes more than 1 subject-reported attack, the duration is calculated from the start of the first subject-reported attack to the end of the last subject-reported attack that has been combined into 1 attack. A similar adjustment for duration will be made for adjusted subjectreported attacks that are combinations of two or more subject-reported attacks in Part 3. The duration of the attack from start of the attack to time that the worst was over will also be calculated and summarized.

# 6.7.5.6. Attack Onset Relative to Prior Dose of Study Drug

For each confirmed on-treatment attack, the time to attack onset from the time of the prior dose of study drug reported in the subject CRF page will be calculated. If there is no dosing time reported for the dose taken prior to the attack, the attack onset time relative to prior dose will be missing. The attack onset time relative to prior dose of study drug is information is used in the listing of attack data only.

#### 6.7.5.7. Medications to Treat HAE Attacks

The following medications reported as taken as acute treatment in the subject diary or androgens listed as acute treatment in the concomitant medications log will be classified in the analyses as targeted medications to treat subject-reported HAE attacks: Androgens, Berinert, Cinrzye, Kalbitor, Firazyr, Ruconest, fresh frozen plasma. Other medications listed in the diary for treatment of HAE attacks will be considered non-targeted medications to treat subject-reported HAE attacks.

#### 6.7.5.8. Attack Symptoms

Symptoms reported for confirmed on-treatment attacks will be included in summaries of attack characteristics. In addition, listings of diary data will show symptoms for all attacks, whether subject-reported or investigator-confirmed.

#### 6.7.5.9. Attack Location

The location of each subject-reported and confirmed on-treatment attack will be determined based on the symptoms indicated in the e-diary as shown in Table 10.

Abdominal-Only Attack	Mixed Attack	Peripheral Attack (Inclusive of Skin and Airway Swelling)
Symptoms checked must only come from this box: Internal swelling or symptoms of internal swelling in the abdomen: • Nausea • Abdominal discomfort • Cramps (colicky pain) • Vomiting • Abdominal pain • Diarrhea a	Must have at least 1 symptom from left and right box (from abdominal and peripheral attack characterization)	Symptoms checked must only come from this box: Visible swelling: • Face/head • Neck (outer swelling) • Legs, buttocks/genitals • Eyes • Arms • Feet • Stomach (outside) • Mouth/tongue/lips • Hands • Chest/back • Joints Internal swelling or symptoms of internal swelling in the airways: • Lump in throat/tightness • Change in voice • Difficulty swallowing • Difficulty breathing • Pink rings (erythema marginatum) a

 Table 10:
 Determination of Attack Location Using Symptoms Collected in the e-Diary

Note: headache and fatigue symptoms may be checked but play no role in characterization of a subject-reported or confirmed attack

a Diarrhea, erythema marginatum, headache, and/or fatigue cannot be selected alone or in combination without another symptom(s) of swelling or internal swelling to be considered a confirmed attack.

#### 6.7.5.10. Attack Triggers

All attack triggers for each subject-reported attack will be included in listings of attack data.

#### 6.7.5.11. AE-QoL

The AE-QoL (Weller, Groffik et al. 2012) consists of 4 domains and a total score. Each item answered by the subject scores between 0 and 4 points depending on the answer option chosen by the subject. The first answer option gets 0 points, the second option 1 point, the third option 2 points, etc.

Dimensions	Item	
	1. Impairment of work	
Functioning	2. Impairment of physical activity	
	3. Impairment of spare time activities	
	4. Impairment of social relations	
	6. Difficulties of falling asleep	
Fatigue/mood	7. Waking up during the night	
Taligue/mood	8. Feeling tired during the day	
	9. Difficulties in concentrating	
	10. Feeling downhearted	
	12. Feeling burdened at having swellings	
	13. Fear of new suddenly appearing swellings	
Faars/shama	14. Fear of increased frequency of swellings	
reals/shame	15. Ashamed to visit public places	
	16. Embarrassed by the appearance of swellings	
	17. Fear of long term negative drug effects	
Nutrition	5. General limitations in foods and eating	
	11. Limitations in the selection of food and beverages	
Total score	Items 1 to 17	

The AE-QoL domain scores and the AE-QoL total score are calculated using the following formula:

$$(\Sigma items) \div (\max \Sigma items) \times 100$$

where

 $\Sigma$  items = Sum of reported item scores per CRF

Max  $\Sigma$  items = Sum of the maximum possible score for each domain

The calculated AE-QoL ranges from 0 (best) to 100 (worst).

Since only answered items are included in the computation (and the calculated domain and total scores are not raw scores but linear transformations to a 0 to 100 scale), the calculated scores are not highly influenced by missing items. An AE-QoL domain score should not be calculated if more than 1 item is left unanswered in that domain. The AE-QoL total score should not be calculated if more than 25% of items (> 4 items) are left unanswered. Note that subjects who do not work were instructed to leave question 1 blank. As long as that is the only question in the functioning domain that is missing, the functioning domain can still be calculated.

